Patients who decide to start or stop edaravone or riluzole after screening and before randomization, will no longer be eligible to be randomized and should not be followed subsequently. If a patient decides to start edaravone or riluzole after randomization, they will be terminated from taking study medication once that is known by the site. They should return to the clinic for their early drug termination visit as soon as possible following last dose of study drug taken and return 28 days after last dose taken for the Follow-Up Visit. They will not be followed thereafter.

For patients who terminate early from the study and do not want to return to the clinic for the visits as described in the above paragraph, phone call visits should be performed to collect the information if the patient is willing (see [Section 5.8](#)).

Notification of discontinuation will immediately be made to the Sponsor's Medical Monitor. In case of withdrawal of study participation, efforts will be made to perform Early Termination ([Section 5.8](#)) and Follow-Up visit assessments ([Section 5.7](#)). The date the patient is withdrawn from the study and the reason for discontinuation will be recorded on the patient's eCRF. All patients who prematurely discontinue from the study for AEs will be followed for up to 30 days, until the AE resolves, or until the unresolved AE is judged by the Investigator to have stabilized.

The primary reason for a patient prematurely withdrawing from the study should be selected from the following categories and documented in the source documents:

- a. Patient Death
- b. Adverse Event: One or more clinical or laboratory events which, in the medical judgment of the Investigator, are grounds for discontinuation even if the event does not appear to be related to study medication. The patient may withdraw because of an AE even if the Investigator does not feel that the event is grounds for discontinuation.
- c. Protocol Violation: The patient's findings or conduct failed to meet the protocol entry criteria or failed to adhere to the protocol requirements

- d. Patient Withdrawal of Consent: Patient desires to withdraw from further participation in the study and reason for doing so.
- e. Administrative/Other: Any cause of premature termination from the study other than the above, such as illness of investigator, loss of study drug, or termination of study by the Sponsor.

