7.9.2. Time-To-Event Analysis for Muscle Strength

Time-to-event analysis will be performed for muscles that had a measurable muscle strength at baseline. The muscle strength measured by HHD will be analyzed using proportional hazard Cox regression model. The event is defined as muscle strength as measured by HHD equals 0 from any muscle in the evaluated muscle groups. For patients who had the event, the date of muscle strength reached 0 will be used as the event date. For patients who did not have the event, data will be censored at their last date of study visit. Kaplan-Meier method will be used to summarize the time to event, and median, 95% CIs of the median, Q1, Q3, and range will be provided.

7.9.3. Evaluation of SVC Measured at Home Using SVC Measured in Clinic as the Standard

In addition to performing SVC assessments in clinic, GoSpiro home spirometer was given to patients for collecting their SVC data weekly from home. However, the usage of the spirometer varies among patients due to different reasons (eg, patients forgot to take the assessments or had technical difficulties, etc.). Hence it is of interest to evaluate consistency of the SVCs measured at home vs. the SVCs measured in clinic. Also, there may be potential learning effect due to more frequent use of the spirometer that may resulting in higher SVC assessed later on. The analyses to be used for the evaluations are described in the following sections.

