7.9.3.1. Correlation Between at Home and in Clinic Assessments of SVC

The test-retest reliability of SVC measured at home will be assessed using the measures in clinic as the standard for each patient. Each measure at home will be paired with a measure in the clinic within a seven-day of window. Correlation between at home and in clinic SVC assessments overall and by visit will be evaluated using Pearson correlation coefficient and paired t-test.

7.9.3.2. Change from Baseline to Week 12 in Percent Predicted SVC Assessed at Home and in Clinic

The SVC assessed at home and in clinic will be combined for a supportive analysis of change from baseline to Week 12 in percent predicted SVC. A MMRM will be used for the analysis. The response variable will be the change from baseline to each post baseline visit up to Week 12. The model will include the following covariates:

- Treatment (reldesemtiv 300 mg/day, 600 mg/day and 900 mg/day, and placebo)
- Location of SVC collection (at home or in clinic)
- Baseline (baseline value of the response variable)
- Pooled site
- Time (time from the first dose, a continuous variable)
- Riluzole and edaravone use status at baseline
- Baseline-by-time interaction
- Treatment-by-time interaction

An unstructured variance-covariance structure will be used to model the within-subject errors. If a model fails to converge, other covariance matrix structures (eg, compound symmetry) may be used instead of the unstructured covariance matrix. Least square means and the corresponding standard errors, 95% CIs and p-values will be presented.

7.9.3.3. Time to Event Analysis of Percent Predicted SVC Decline to Less Than 50%

To evaluate consistency of the SVCs measured at home vs. that measured in clinic, percent predicted SVC collected during clinic visits and at home will be analyzed using a proportional hazard Cox regression model. The event is defined as percent predicted SVC decline to less than 50% during the 12 weeks of the study. For patients who had the event, the first date of SVC less than 50% will be used as the event date. For patients who did not have the event, data will be censored at their date of study visit or Week 12 visit, whichever is earlier. Kaplan-Meier method will be used to summarize the time to event for percent predicted SVC measured in clinic and at home, separately. The median of the time to event, 95% CIs of the median, Q1, Q3, and range will be provided.

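### SAP 7.9.3.3 censors the home SVC series at a clinic-visit date, so weeks without a home test count as event-free and home risk looks lower than clinic risk

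*SAP*

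**What the plan says.** **Home and clinic SVC (SAP 7.9.3.3).** The stated purpose is "To evaluate consistency of the SVCs measured at home vs. that measured in clinic". The endpoint is set as follows: "The event is defined as percent predicted SVC decline to less than 50% during the 12 weeks of the study". There are two curves: "Kaplan-Meier method will be used to summarize the time to event for percent predicted SVC measured in clinic and at home, separately". There is one censoring rule for event-free patients: "data will be censored at their date of study visit or Week 12 visit, whichever is earlier". It does not say which study visit is meant, and it does not mention the last evaluable SVC of either kind.

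**Home testing is expected to be incomplete.** SAP 7.9.3 says "the usage of the spirometer varies among patients due to different reasons" and gives forgotten tests and technical difficulties as examples. SAP 7.9.3.4 plans a comparison with patients who never used the home device. Protocol 5.14.1 and Appendix A make home SVC conditional on the device being suitable in the region.

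**Study visits are clinic visits.** Protocol 3.1 lists seven: Screening, Day 1, Weeks 2, 4, 8 and 12, and Follow-Up. Weekly home tests are not among them.

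**Muscle strength (SAP 7.9.2).** The event is an HHD strength of 0. The rule is similar: "For patients who did not have the event, data will be censored at their last date of study visit". It refers to the visit, not to the last HHD result.

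**The concern.** Kaplan-Meier and Cox methods treat a patient as under observation up to the censoring date. An SVC below 50% at home can be seen only if the patient tests at home. Once home testing stops, that patient can have no home event, yet under 7.9.3.3 stays in the home risk set until a clinic-visit date, usually Week 12. The number of events is unchanged while the risk set is too large, so the estimated home risk is too low.

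The clinic series has little of this problem, because SVC is scheduled at every visit. The bias is therefore uneven between the two series being compared. A perfectly accurate home device would show fewer events than the clinic, and the analysis could not separate device disagreement from missed testing. Giving both series the same schedule, or enrolling more patients, would not remove this.

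**Working it through.** **What there is to reproduce.** The documents give no event rate, event count, home-testing completeness or power for either time-to-event analysis. The only sizing is for the primary contrast and has no bearing here. The sizes below rest on assumed rates.

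**Assumptions.** Constant hazard; home and clinic agree perfectly; true 12-week risk *r*; a fraction *f* of patients stop home testing at times uniform over 12 weeks, unrelated to risk; a fraction *g* never test at home. All keep attending clinic, so the rule censors them at Week 12.

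**Formula.** Let H = −ln(1 − r) be the 12-week cumulative hazard. A patient who stops at a uniform time has an observed home event with probability s = 1 − r/H. A never-user has probability 0. Everyone without an event is carried to Week 12, so the Kaplan-Meier risk equals the observed proportion:

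home risk under the rule = (1 − f − g)·r + f·s

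**Numbers for r = 10%.** H = 0.10536 and s = 1 − 0.10/0.10536 = 0.0509.

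| f | g | Calculation | Home risk |
|---|---|---|---|
| 20% | 0 | 0.8 × 0.10 + 0.2 × 0.0509 | 9.0% |
| 40% | 0 | 0.6 × 0.10 + 0.4 × 0.0509 | 8.0% |
| 60% | 0 | 0.4 × 0.10 + 0.6 × 0.0509 | 7.1% |
| 40% | 20% | 0.4 × 0.10 + 0.4 × 0.0509 | 6.0% |

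The last row applies only if never-users are kept in the home series.

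**Check with real test schedules.** A simulation of 200,000 patients per scenario used weekly home tests, some weeks skipped, and a true risk of 10%.

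| Never-users | Stop early | Weeks skipped | SAP rule | Censor at last home test |
|---|---|---|---|---|
| 0 | 10% | 0 | 9.6% | 10.1% |
| 0 | 25% | 10% | 8.8% | 10.1% |
| 10% | 25% | 10% | 7.8% | 10.0% |
| 20% | 40% | 20% | 6.2% | 10.1% |
| 30% | 50% | 20% | 5.1% | 10.1% |

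True risks of 5% and 20% gave the same pattern. For the clinic schedule (Weeks 2, 4, 8, 12), with 5–10% lacking later measurements and 2–5% of assessments missed, the visit-date rule gave 9.2–9.5% against 9.9–10.0%. That overstates the clinic shortfall, since it carries every such patient to Week 12.

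**If sicker patients stop first.** Take f = 40%, g = 0, with stoppers at three times the hazard of the rest, who have a 10% risk.
- True risk: 0.6 × 0.10 + 0.4 × (1 − 0.9³) = 16.8%.
- SAP rule: for stoppers 3H = 0.3161 and s = 1 − 0.271/0.3161 = 0.1426, so 0.6 × 0.10 + 0.4 × 0.1426 = 11.7%.
- Censoring at the last home test: 14.1%.

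The change removes 2.4 of the 5.1 points of bias (14.1 − 11.7 and 16.8 − 11.7).

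**HHD ceiling.** Take an assumed true risk of 40% and let all of the planned 10% dropouts move to phone contact at uniform times with the same hazard. Then H = 0.5108, s = 1 − 0.40/0.5108 = 0.2170, and the rule gives 0.9 × 0.40 + 0.1 × 0.2170 = 38.2%.

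**The case against.** **Never-users may not be in the home series.** No sentence in 7.9.3.3 puts patients without a home reading into it, and none takes them out. SAP Table 2 assigns the Section 7 efficacy analyses to the FAS, which requires some post-baseline efficacy assessment but not a home SVC; that favours inclusion without settling it. The 6.0% figure is therefore conditional. The 9.0% to 7.1% range does not need never-users.

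**The HHD part is weak.** This largely stands. HHD is scheduled at every study visit and at Early Termination, so visit date and last HHD date normally coincide. SAP 5.5.8.3 records 0 for a patient too weak to perform the test, which makes it an event. A gap opens only if the last visit is one without HHD or is a phone contact. Protocol 5.15 does say "phone call visits should be performed to collect the information if the patient is willing", and the phone list in Protocol 5.8 has no dynamometry. But SAP 5.6.4 and 6.1 distinguish the last visit from the last contact, so phone contacts need not count as visits.

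**Stronger inferences that the documents do not support.**
- A reader might infer that home events would also be seen later. Home tests are weekly and clinic tests are at Weeks 2, 4, 8 and 12. With 40% stopping and a 10% risk, simulation puts the mean detection time of observed events at Week 5.9 at home and Week 7.6 in clinic: fewer home events, but not later ones.
- A reader might infer that censoring at the last reading always recovers the true risk. It does so only if stopping is unrelated to risk.
- A reader might infer that dose hazard ratios are shifted. That would need non-use or discontinuation to differ by arm, and the documents give no sign of it.

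**Agreement is examined elsewhere.** SAP 7.9.3.1 pairs home and clinic readings within seven days, and 7.9.3.2 fits a combined model with a location term. This limits the consequence but does not make 7.9.3.3 interpretable.

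**Conclusion.** The point holds for the home series in 7.9.3.3. Read as written, the rule counts untested home weeks as event-free and biases home risk below clinic risk in the one comparison the analysis is meant to make. The direction follows from the rule whenever patients stop home testing while still attending clinic. The size cannot be derived from the documents: the figures depend on assumed rates of stopping, never-use and events, on constant hazard, and on stopping unrelated to risk.

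For 7.9.2 the effect is small and conditional: 40% reading as 38.2% is a ceiling under equal hazard. Both analyses sit under exploratory analyses, outside the closed testing procedure in SAP 7.4, so primary and secondary conclusions are unaffected. The change is still worth making before database lock, because the analysis would otherwise not answer its own question.

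**What to change.** In SAP 7.9.3.3:
- Censor event-free patients in the home series at the last evaluable home SVC, and in the clinic series at the last evaluable clinic SVC, each on or before Week 12. This also removes the uncertainty over which study visit is meant.
- Limit the home series to patients with at least one evaluable home SVC.
- State that the analysis assumes non-informative stopping of home tests, and that if sicker patients stop first the bias is reduced but not removed.
- Say how home evaluability is judged in weeks without a clinic visit. SAP 5.5.8.1 defines it against a clinic SVC from the same week, so the last evaluable home SVC is otherwise not fully defined.

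As a minor matching edit, censor 7.9.2 at the date of the last HHD assessment.

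Cost: a few sentences of SAP text and a changed derived censoring date, with no new data. The home series loses some person-time, so its confidence intervals widen somewhat.

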5.14. Clinical and Pharmacodynamic Outcome Measures

5.14.1. Pulmonary Function Assessment

The pulmonary function assessment in this study will be SVC. Pulmonary function assessment will be performed at each study visit as described in the Study Manual. Patients will also perform home SVC assessments weekly through the course of the study following Day 1 (if the device is suitable for use in that region) as described in the Study Manual.

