8.1.2. Sample Size and Randomization

Approximately 445 patients will be randomized to receive either one of the three CK-2127107 doses (300 mg/day, 600 mg/day and 900 mg/day TDD) or matching placebo tablets in a ratio of 1:1:1:1. Randomization will be stratified by riluzole use/non-use and edaravone use/non-use. The dropout rate at Visit Week 12 is estimated to be 10%, thus approximately 400 patients are expected to complete 12 weeks of double-blind treatment. The effect of CK-2127107 on the change from baseline to Week 12 in percent predicted SVC will be analyzed using a mixed model for repeated measures (MMRM) with the contrast (-5, -1, 3, 3) to reflect the assumed relationship for the placebo, 300 mg/day, 600 mg/day and 900 mg/day dose groups. The analysis is estimated to provide 90% power to detect 2.75, 5.5 and 5.5 percentage points advantage over placebo for the 300 mg/day, 600 mg/day and 900 mg/day CK-2127107 dose groups, respectively, in change from baseline of percent predicted SVC, at the end of the double-blind treatment (Visit Week 12). This calculation is based on a two-sided test with alpha set at 0.05 and a common standard deviation of 14 percentage points.

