7.9.3.4. Comparing Percent Predicted SVC Between Patients Who Used a Home Spirometer for SVC Assessments and Those who Never Used

To evaluate the potential learning effect of using a spirometer and its impact on the percent predicted SVC measured in clinic, the use of the spirometer will be added as a covariate in the MMRM for a supportive analysis of change from baseline to Week 12 in percent predicted SVC and be evaluated for if it's a significant factor in predicting the outcome. The rates of decline (ie, slope) in percent predicted SVC assessed in clinic will also be compared between patients who performed SVC assessments using the home spirometer and those who did not use. In addition, since SVC will be assessed 3 times in each clinic visit, the variation among the 3 measurements collected at each visit will be compared between patients who used the home spirometer for SVC assessments and those who did not use.

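### The home-spirometer learning check (SAP 7.9.3.4) compares non-randomised groups formed after Day 1 without adjusting for progression, so a significant use term could reflect prognosis rather than learning

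*SAP*

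**What the plan says.** SAP 7.9.3.4, within the exploratory analyses of SAP 7.9, aims to find out whether practice on the home device raises SVC measured in clinic. It has three parts:

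- **MMRM.** "the use of the spirometer will be added as a covariate in the MMRM for a supportive analysis", with a check of whether use is a significant predictor of change to Week 12.
- **Slope.** Rates of decline in clinic SVC are "compared between patients who performed SVC assessments using the home spirometer and those who did not use" it.
- **Variation.** The spread of the three readings at each clinic visit is compared between the same groups.

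The section title contrasts users with those who never used the device. No usage threshold or time window is given.

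On why use differs, SAP 7.9.3 says "the usage of the spirometer varies among patients due to different reasons", giving forgetting and technical difficulties as examples. Protocol 5.14.1 adds a further source: home testing is done "if the device is suitable for use in that region".

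On timing, Protocol 5.1 places randomisation before the first dose on Day 1. Protocol 5.2 places device training on Day 1 and weekly home testing after it.

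On adjustment, the primary MMRM (SAP 7.5.1) contains treatment, baseline SVC, pooled site, visit, riluzole and edaravone use, and the treatment-by-visit and baseline-by-visit interactions. SAP 5.5.7 derives a pre-study progression rate and SAP 7.3 uses it for subgroups, but 7.9.3.4 does not mention it.

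**The concern.** Learning is a causal question, and ever-use of the device is an observed behaviour. Users and never-users may differ in how fast they decline for reasons unrelated to practice. For example, a patient who is losing function quickly may manage a home device less well, and one who leaves early has fewer weeks in which to become a user. Both are plausible inferences; neither document states them.

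If either holds, users would show a better Week 12 change and a shallower slope even if practice did nothing. The SAP's criterion, a significant use term, cannot tell the two explanations apart. At stake is how a reader interprets the measurement behind the primary endpoint: a false learning signal would suggest that clinic SVC is inflated by home practice.

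**Working it through.** **1. The plan's own figure.** The plan gives no figure for the learning analysis, so I checked the SD and sample-size framework that it borrows. Inputs (Protocol 8.1.2): two-sided alpha 0.05, SD 14, contrast (-5, -1, 3, 3), effects 0, 2.75, 5.5 and 5.5, and about 400 completers in four equal arms.

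- Contrast value: -5(0) - 1(2.75) + 3(5.5) + 3(5.5) = 30.25
- SE: 14 × √(44/100) = 9.287
- Ratio: 30.25/9.287 = 3.257
- Power: Φ(3.257 - 1.960) = 90.3%, against 90% stated. It reproduces.

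**2. Size of a false use difference, with zero learning.** The FAS count comes from the SAP Appendix C pools: 20 + 53 + 49 + 52 + 61 + 71 + 51 + 36 + 65 = 458 (36 is the sum of the site counts in pool 8). SD is 14. The never-user share p and the correlation r between propensity to use and 12-week change are **assumptions**. Because the MMRM already contains baseline SVC and site, r must be read as the correlation left after those covariates.

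With a normally distributed propensity cut at c = Φ⁻¹(p):

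- False difference d = 14 × r × φ(c) × [1/p + 1/(1-p)]
- SE = 14 × √[1/(458p) + 1/(458(1-p))]
- Chance of significance = Φ(d/SE - 1.96) + Φ(-d/SE - 1.96)

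Example, p = 0.25 and r = 0.1: d = 14 × 0.1 × 0.3178 × 5.333 = 2.37; SE = 1.51; d/SE = 1.57; chance 35%.

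| p | SE | r = 0.05 | r = 0.1 | r = 0.2 |
|---|---|---|---|---|
| 15% | 1.83 | 1.3 points, 11% | 2.6 points, 29% | 5.1 points, 80% |
| 25% | 1.51 | 1.2 points, 12% | 2.4 points, 35% | 4.7 points, 88% |
| 40% | 1.33 | 1.1 points, 14% | 2.3 points, 39% | 4.5 points, 92% |

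**3. The same question by assumed difference in decline.** Take 400 completers with 20% never-users, so SE = 14 × √(1/80 + 1/320) = 1.75. The use term is significant in 5% of trials if never-users decline no faster, 9% if 1 point faster, 35% if 2.75 points, 63% if 4 points and 88% if 5.5 points.

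**4. Do the existing covariates protect?** This was simulated with a Week 12 ANCOVA as a simplified stand-in for the MMRM. It contained use, baseline SVC, nine sites and arm, with 400 patients, 20% never-users, 1,500 runs and zero learning. Latent progression was assumed to contribute an SD of 7 points.

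| What drives non-use | Mean false effect (points, absolute) | Significant |
|---|---|---|
| Chance | 0.0 | 4.7% |
| Baseline SVC | 0.1 | 4.2% |
| Region | 0.1 | 5.3% |
| Unmeasured progression, odds ratio 1.4 per SD | 2.4 | 25% |
| Unmeasured progression, odds ratio 2.0 per SD | 4.5 | 74% |
| Unmeasured progression, odds ratio 3.0 per SD | 6.5 | 96% |

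The covariates remove bias from the factors they represent and leave bias from progression. The sizes depend on the assumed 7-point SD, so only the direction and the contrast between rows should be relied on.

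**The case against.** The strongest reply is that the documented reasons for non-use are benign. Forgetting and technical trouble may be close to random, and device suitability is regional. Baseline SVC and pooled site are already in the MMRM, and under those mechanisms the simulated false-positive rate stays near 5%. The analysis is labelled supportive and sits outside the testing hierarchy of SAP 7.4. All of this stands. It limits the point to a conditional one about an exploratory check.

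A reader might infer more than the documents support:

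- **That use is a patient's choice and never-users are sicker.** Neither document says so. Could is supported; will is not.
- **That severity is not adjusted for at all.** The MMRM includes baseline SVC. The gap there is progression. The slope and variation comparisons are more exposed because 7.9.3.4 names no covariates for them; the SVC slope model in SAP 7.7 has baseline and pooled site, but 7.9.3.4 does not say that it applies.
- **That a false learning signal is very likely.** At a residual correlation of 0.1, most trials (61-71%) would show nothing significant.
- **That the primary result is in doubt.** The primary model has no use term, and practice common to all arms would cancel in the comparison between arms.
- **That the treatment estimate in the supportive model is distorted.** That needs treatment to affect use, or use and decline to share causes. If a single home test makes a user, testing that starts straight after Day 1 leaves treatment little time to change the classification. The risk is plausible but unquantified, which justifies caution and no more.

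**Conclusion.** The point holds as a limit on interpretation and a gap in adjustment. As specified, a significant use term or slope difference cannot be read as learning, because ever-use is not randomised, forms after Day 1, and is not adjusted for progression.

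The possible size is 2.3-2.6 points at a residual correlation of 0.1 and 4.5-5.1 points at 0.2. For scale, the sample size rests on drug effects of 2.75 to 5.5 points. These figures assume no true learning, SD 14, 458 patients, 15-40% never-users and an association with progression that survives the MMRM covariates. The documents supply only the SD and the patient count. If non-use is random, regional or explained by baseline SVC, the bias is negligible.

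**What to change.** Amend SAP 7.9.3.4 as follows:

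1. Add baseline ALSFRS-R total score and the pre-study progression rate (SAP 5.5.7) as covariates, both in the MMRM containing use and in the slope comparison.
2. Tabulate users and never-users by these two variables and by pooled site.
3. Compare the groups on Screening-to-Day 1 change in clinic SVC, which precedes any home use. The interval is at most 14 days (Protocol 5.9), so a null result is weak reassurance.
4. State that the use term will be interpreted as an association, not as learning.
5. State that no treatment-effect conclusion will be drawn from the model containing use.

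Do not replace use with regional availability of the device. In Appendix C every pool except pool 2 lies within one country. If suitability is set by country (an assumption, since region is not defined), only those 53 of 458 patients could vary in availability within a pool, so the term would be largely collinear with pooled site.

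The cost is SAP wording and slightly more analysis work; all the data are already scheduled. Residual confounding remains, because the pre-study rate only approximates progression on study.
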